NCT04112173

Fall-recovery training for those with chronic stroke and low falls self-efficacy

Study Protocol and Statistical Analysis Plan

9/18/2019

1. Protection of Human Subjects

a. Human Subjects Involvement, Characteristics, and Design

This feasibility study has a single-arm, repeated measures design in which a non-active control period is followed by an intervention period. In other words, there are three assessment visits (baseline, assessment after non-active control period, and assessment after experimental intervention).

A total of five participants with chronic stroke (i.e. 6 or more months after stroke) are expected to qualify for this study. All participants must have low balance self-efficacy, as determined by an Activities-Specific Balance Scale (ABC) score less than 68. We plan to enroll an additional two participants, anticipating that these participants will not be eligible to continue in the study after the initial DXA and physical therapist screening.

All in-person activities will occur at the University of Delaware.

b. Study Procedures, Material, and Potential Risks

Proposed involvement of human subjects will include the following:

1. Study participation requires nine laboratory visits. Assessment visits will take up to four hours. Training visits will take one to two hours.
2. Upon enrollment, the Fugl-Meyer Lower Extremity assessment and the Stroke Impact Scale will be administered to characterize participant impairment.
3. We will record the height, mass, and age of all participants.
4. Study staff will provide an initial screening to ensure that potential participants meet the inclusion and exclusion criteria.
5. If the participant is over the age of 50 years, his or her bone mineral density will be measured from dual-energy X-ray absorptiometry (DXA; Delphi W; Hologic, Inc.). Subjects will not be allowed to continue with the study if they have a total hip or femoral neck bone mineral density t-score < -2.5. The left hip will be evaluated unless the subject has had a left hip replacement. If both hips have been replaced, then the participant will not continue in the study. DXA scans will be performed by a State of Delaware certified radiation technician.

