- An Activities-Specific Balance Confidence (ABC) score less than 68. Exclusion criteria (all self-reported)
- More than one stroke
- Acute illness at the time of functional assessment or training
- Body mass greater than 136 kg (300 lbs) to ensure that the treadmill accelerates accurately
- Lower extremity joint replacement or shoulder joint replacement within a year prior to participation
- Dementia
- Parkinson's disease
- A history of back surgery
- A history of neck surgery
- More than one occurrence of back or neck pain in the month prior to participation
- Current back or neck pain at the time of participant enrollment
- Bulging vertebral discs
- Spine, hip, or lower extremity fracture within a year prior to participation
- Open lesions on the lower extremity
- Insulin-dependent diabetes
- Use of a pacemaker
- Use of an ostomy pouch
- Pregnancy
- Osteoporosis
- The inability to stand and walk independently or with the assistance of a cane.
- Doctor recommendation to avoid moderate physical activity or exercise
- Any neural, muscular, or skeletal condition or injury that precludes safe participation in the training or introduces a confounding factor on the study, at the discretion of the clinician or study staff

Materials

Data sources will include anthropometric measurements, clinical measures of function, balance and mobility, stepping thresholds (a measure of reactive postural control), questionnaires about falls self-efficacy, depression, and physical activity, walking activity from step counters, and questions from interviews. All data will be acquired solely for research purposes. All materials will be identified by a subject-specific code, the key of which will be stored as a password protected file on a secure computer or server and/or in locked cabinets within the locked laboratory.

Potential Risks

It is possible that subjects could fall to the floor during assessments of mobility and balance. All participants will wear a harness attached to an overhead rail while on the treadmill. To minimize the risks of a fall during other assessments of balance and mobility, all subjects will be appropriately guarded using standard clinical judgment of safety procedures (e.g. use of a gait belt and/or harness system when needed, proper positioning of the rater relative to the subject, etc.).

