For this study we will recruit seven individuals with chronic stroke from Delaware and adjacent areas in Maryland, Pennsylvania, and New Jersey. Subjects who complete the *Shared Pre-enrollment Process for Stroke Research Team Studies* protocol will be invited to participate in this study. The pre-enrollment study is a recruitment arm of the UD Stroke Registry. This registry advertises its studies through local media sources, social media, community outreach, and word of mouth.

Potential participants will be contacted by phone to explain the study, discuss and confirm inclusion and exclusion criteria, answer questions, and invite participation. If an individual is interested in participating, they will be invited to STAR Campus for the first study visit.

At this study visit, a member of the study team will guide the potential participant through an informed consent document, answering questions that the individual may have. Once written consent has been attained, the participant will be enrolled in our study.

b. Protection Against Risks

If immediate medical treatment is needed for any study related injury or adverse experience, the study Physical Therapist will evaluate the participant. If needed, the STAR campus emergency response protocol will be activated and first responders will come to the laboratory.

Each participant will be told that he/she has the alternative to not participate in this study, and that the choice to end participation will not jeopardize his/her medical care. The honorarium for the visit will still be paid. Insurance will not be charged.

All data are coded and no identifying information is used in any analyses or publication. A key linking identifiable data to subject codes will be stored as a password protected file on a secure computer or server, with physical copies stored in locked cabinets within a locked laboratory. We adhere to all HIPAA privacy rules that affect research protocols.

No study staff are qualified to clinically interpret incidental findings from the DXA scan. At the request of the participant, we will provide them with a printed copy of the DXA scan results that they can bring to their physician.

3. Potential Benefits of the Proposed Research to Human Subjects and Others

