The potential benefits associated with the project outweigh the risks of participation. Participants may learn more about their capabilities through participation in the assessments. Participants who receive a DXA scan may learn more about their bone density. The general knowledge gained by this study may inform hypotheses for subsequent studies to more rigorously evaluate the benefits of our exercise intervention on falls self-efficacy and walking activity. In addition, the current study will inform modifications to our approach to improve its feasibility. The participant-specific and general knowledge benefits outweigh the risks described earlier, including muscle soreness and nervousness/excitement. These risks are experienced in everyday life with the introduction of a new exercise program and when in

situations where balance may be challenged. However, in our study, the risks of falling to the floor or ground have been reduced by a safety harness and appropriate guarding from study staff.

4. Importance of the Knowledge to be Gained

We may develop methods to improve reactive postural control, increase balance self-efficacy, and enable walking activity in those with chronic stroke and low falls self-efficacy. If we are able to do so, then we may identify a pathway to enable walking activity, in turn improving the quality of life and healthspan of this population. These benefits outweigh the risks of participation, which align with risks of starting many other exercise programs (e.g. soreness, risk of loss-of-balance, nervousness/excitement).

Statistical Design and Power

This feasibility study has a single-arm, repeated measures design in which a non-active control period is followed by an intervention period. In other words, there are three assessment visits (baseline, assessment after non-active control period, and assessment after experimental intervention).

We expect to enroll seven participants into this study (Figure 1). Of these participants, we estimate that two will not pass initial screening from the physical therapist or DXA scan. Note that, in order to adhere with IRB and Radiation Safety guidelines, we must enroll participants before performing this screening.

The aim of this study is to demonstrate that fall-recovery training is feasible in stroke survivors with low falls self-efficacy. As per feasibility-study guidelines, we will gather evidence of the following:

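### A hip T-score below -2.5 ends participation, but the protocol's only stated route to that result is a printout given if the participant asks

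*Combined protocol and SAP*

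**What the plan says.** Section 1.b, item 5, sets out who is scanned: "If the participant is over the age of 50 years, his or her bone mineral density will be measured". It then gives the stopping rule, under which participants "will not be allowed to continue with the study if they have a total hip or femoral neck bone mineral density t-score < -2.5". Item 5 has a second, separate stopping rule for people with both hips replaced.

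Section 2.b (Protection Against Risks) deals with what happens to the scan result. It states that "No study staff are qualified to clinically interpret incidental findings from the DXA scan" and that, upon "the request of the participant, we will provide them with a printed copy of the DXA scan results that they can bring to their physician".

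Three other places bear on the point:

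- The exclusion list in section 1.b is introduced as "Exclusion criteria (all self-reported" and includes osteoporosis.
- Section 2.a describes two contacts before the scan. In the first, "Potential participants will be contacted by phone to explain the study, discuss and confirm inclusion and exclusion criteria". In the second, at the first visit, staff "guide the potential participant through an informed consent document".
- Section 3 names learning about one's bone density as a possible benefit for those scanned, but sets out no procedure for it.

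The Statistical Design and Power section explains that enrolment has to come before the DXA and physical therapist screens. Of seven enrolled, "we estimate that two will not pass initial screening from the physical therapist or DXA scan".

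**The concern.** The T-score is a planned screening measure with a fixed cut-off, and the study uses it to decide that a person should not be trained. The written rule nevertheless makes release of the result depend on that person knowing to ask.

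The people stopped by the scan are also those least likely to know to ask. Osteoporosis is a self-reported exclusion confirmed by phone, so someone who knows of the condition and reports it should not reach the scanner. Those first caught by the scan are people who did not report it, and some may be unaware of low bone density.

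What is at stake is whether a consented participant leaves with information that could usefully go to a physician. Nothing in the feasibility evidence or the effect sizes depends on it.

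**Working it through.** The plan states no figure on this point to reproduce, so the check is mainly a comparison of texts.

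**Step 1. When does the study act on the result?** Section 1.b, item 5: a total hip or femoral neck T-score below -2.5 in a scanned participant (over 50) ends participation.

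**Step 2. When does the participant receive the result?** Section 2.b: a printed copy, on request. Three things were looked for elsewhere in the supplied text: a statement that an excluded participant is told the reason, an unprompted offer of the printout, and a referral to a physician. None was found. Section 3 expects that scanned participants may learn about their bone density but does not say how.

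**Step 3. Could an earlier step supply the result?** The order is phone call, consent and enrolment, then scan. The call and the consent discussion can make the exclusion rules known, which makes an unexplained exit less likely. Both come before the scan, so neither can convey the participant's own T-score.

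**Step 4. What has to happen for someone to leave without the result?** All of the following:

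1. the participant is over 50 and is scanned;
2. the T-score is below -2.5;
3. osteoporosis was not reported at the phone screen;
4. the participant does not ask for the printout;
5. staff do not volunteer the result.

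The text allows this combination but does not make it certain.

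**Step 5. How many people?** Inputs from section 1.a and Statistical Design and Power: 7 enrolled, 5 expected to continue.

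- Expected screen failures: 7 - 5 = 2, for the physical therapist and DXA screens combined. This is a planning estimate; it is neither a cap nor split between the two screens.
- Number scanned: between 0 and 7, depending on how many are over 50. A participant with both hips replaced leaves no hip to evaluate, which does not widen this range.
- T-score exclusions: at least 0 and at most the number scanned, so no more than 7 at planned enrolment.
- Number leaving without the result: not computable from the documents.

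**Step 6. Does the non-interpretation sentence stand in the way?** That sentence concerns clinical interpretation of incidental findings. Saying which pre-set cut-off was met, and handing over a printout for a physician to read, does not require staff to interpret the scan.

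**The case against.** The strongest reply is that the answer may lie in a document not supplied. How scan results are returned is ordinary consent-form content, and the consent pages are not part of the text reviewed. Their absence here is not a gap in the plan. This stands, and it limits the point to the protocol text plus a check against the consent form.

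Second, section 2.b promises the printout on request; it does not say that results are released in no other way. A reader might infer that excluded participants are never told why, or that staff must hold the result back. The documents support neither reading. They do not say whether staff state the reason for exclusion, they do not forbid volunteering the result, and section 3 contemplates participants learning about their bone density. What remains is narrower: request is the only route written down.

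Third, release on request is a defensible choice when no staff member can interpret the scan, and hearing that one has failed a bone-density cut-off may sound like a diagnosis. That is a reason for careful wording and for keeping the non-interpretation sentence. It is not a strong reason to leave the offer unmade, because the printout can be declined and goes to a physician to be read.

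Fourth, the harm is conditional and unquantified. That is correct and is reflected in the severity.

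**Conclusion.** The point holds in a limited form. On the supplied protocol text, a participant stopped because of a T-score below -2.5 who does not ask for the printout could leave without a result that the study itself acted on. Severity is low: this is an inexpensive improvement to participant protection.

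Its size is unknown. A reader might take the two expected screen failures as the number affected, but that figure covers the physical therapist and DXA screens together and says nothing about who would ask or be told. Nor does the point touch any outcome, effect size or feasibility conclusion.

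The conclusion rests on two assumptions: that the consent form does not already provide for an unprompted offer, and that staff follow the written rule without adding to it. If the first is wrong, all that remains is to bring section 2.b into line with the consent form.

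**What to change.** In section 2.b, replace the request rule with:

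> Any participant excluded because of a total hip or femoral neck T-score < -2.5 will be told that this cut-off was the reason and will be offered, without having to ask, a printed copy of the DXA results to take to their physician; other scanned participants will receive a copy on request.

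The wording should be tied to the T-score and not to item 5 as a whole. Item 5 also stops people with both hips replaced, who would otherwise be given a false reason and offered a result they may not have.

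Keep the sentence that staff do not clinically interpret incidental findings, leave the cut-off as it is, and align the consent form if it does not already say this.

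The cost is one protocol sentence, matching consent wording if needed, and a brief conversation with one printed page per participant excluded on T-score. At planned enrolment that cannot exceed seven people.

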6. Falls self-efficacy will be determined by administering the Activities-Specific Balance Confidence (ABC) scale and the Falls Efficacy Scale – International (FES-I). Because the ABC scale dictates group assignment in our study design, this measure also serves as a screening tool.
7. We will administer the following surveys:
 - a. Physical Activity Scale for Individuals with Physical Disabilities
 - b. Center for Epidemiologic Studies Depression Scale (CES-D)
 - c. A survey on the family and friend support for exercise habits
 - d. Barriers to Physical Activity and Disability Survey
8. We will administer the following clinical evaluations:
 - a. Berg-Balance Scale
 - b. Abbreviated Balance Evaluation Systems Test (Mini-BESTest)
 - c. Functional Gait Assessment
 - d. Timed Up-and-Go test
 - e. 10 m walk test
 - f. Six-minute walk test
9. Reactive postural control will be quantified from anterior, posterior, and lateral single-stepping thresholds. Participants will be outfitted with a safety harness attached to an overhead rail. As they stand on a computer-controlled treadmill (ActiveStep®, Simbex, Lebanon, NH), participants will be instructed to “try not to step” in response to rapid

belt displacements. For each directionally-opposed pair of thresholds, a progressively difficult series of movements will be implemented. Here, thresholds are defined as the perturbation magnitudes that consistently elicits one or more steps in a given direction. Within each progression of perturbations, the direction and timing of the belt movement is pseudo-randomized to limit anticipatory adjustments. The progression of perturbations will continue until each opposite-direction threshold is identified, as evident by four consecutive failed responses.

10. Participants will be given a StepWatch™ activity monitor, and will be instructed on how to wear the monitor, when to wear the monitor, and how to return the monitor to the study team. Before leaving, we will ensure that the participant is able to don and remove the monitor strap on their own. Participants will wear the monitor for seven days.
11. After three weeks, participants will repeat all questionnaires, laboratory, and walking activity assessments (Steps 7-11).
12. After this second assessment, participants will undergo six sessions of perturbation-based fall-recovery training. Each session will consist of the following five-minute perturbation series.

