Subjects may experience muscle soreness as a result of participation. Exclusion criteria have been determined in an effort to limit discomfort. In the case of acute soreness, the current training session will be ended, and subsequent sessions will not resume until

soreness has subsided. The perturbation magnitude will not be again advanced to the levels that initiated soreness.

Occasionally, subjects may feel a heightened level of excitement or nervousness during their participation. These feelings are usually due to the anticipation of an oncoming postural perturbation (i.e. there is a delay in time from when the subject says they are ready and the treadmill belts accelerate). A random delay in the perturbation onset, as well as no indication of the upcoming perturbation direction, are maintained in order to improve the ecological validity of the protocol (i.e. people are rarely aware of the timing and direction of a fall before it is initiated). Should the subject express these feelings, they will be given the option to end their participation in the session or study. Furthermore, accommodations such as frequent breaks, minimizing the delay before the perturbation, limiting the size of the perturbation, and allowing subjects to know the perturbation direction beforehand can be made. If the study team member determines that such feelings are unreasonably high, to the point where it precludes safe participation in the study, they will end the subject's participation in that aspect of the study.

During assessments and training sessions, we will stop participation if any of the following conditions occur: a) ataxia, dizziness, or near syncope, b) any chest pain or angina symptoms, c) Signs of poor perfusion cyanosis or pallor, and d) excessive fatigue, excessive shortness of breath, leg cramps, claudication.

For subjects who receive it, the DXA scan is accompanied by a negligible effective dose of radiation (0.001 mSv; www.radiologyinfo.org). This effective dose is less than 0.1% of the dose received from a spine X-ray, and it is comparable to the amount of radiation exposure from three hours in natural surroundings.

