We consider the risks of our treadmill protocols to be minimal. The risks from these protocols are not greater than those encountered with exercise in the free-living environment. A harness system arrests the fall before the subject's hands, knees, or head come into contact with the treadmill. The subject may experience soreness from the harness support or from the required physical activity. The use of a treadmill to deliver perturbations to older adults, young adults, individuals with neuromuscular impairment, and individuals with lower-extremity amputations is well-documented in the literature. We will be using a commercially available, computer-controlled treadmill that is used clinically (CPT Codes: 97750, 97110, 97112, and 97116) for balance assessments and training (ActiveStep, Simbex, Lebanon, NH). [name] and his laboratory have worked with over 250 individuals, including those with chronic stroke, those with lower limb loss, older adults, young adults, typically developing children, and children with cerebral palsy, on the ActiveStep with no serious adverse events or injuries requiring medical attention. Here, serious adverse events are defined as any untoward medical occurrence that results in death, is life threatening, requires inpatient hospitalization or prolongation of existing hospitalization, or results in persistent or significant disability/incapacity.

We expect that those with low falls self-efficacy may frequently rely on a cane to stand and walk. Therefore, we have modified our treadmill protocols to be safe and feasible for use with a cane. Specifically, we have limited the standing perturbation sizes to those just large enough to elicit a step or an adjustment of the cane position. In addition, we have excluded these participants from perturbations delivered as the participant walks on the treadmill.

We see minimal risk of confidentiality—data are coded and no identifying information is used in any analyses or publication. We adhere to all HIPAA privacy rules that affect research protocols.

2. Adequacy of Protection against Risks

a. Informed Consent and Assent

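### None of the three feasibility domains is designed to register harms, and no visit has a stated question on falls, injuries or soreness since the last visit

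*Combined protocol and SAP*

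**What the plan says.** Statistical Design and Power states the aim, to show that the training is feasible in this population, and introduces the evidence with "As per feasibility-study guidelines, we will gather evidence of the following". Three domains follow.

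- **Adaptation**: changes to the protocol, the number and size of perturbations, and adherence.
- **Implementation**: what helped or hindered completion, and what participants found challenging or beneficial.
- **Limited Efficacy**: Cohen's d for changes in self-efficacy and activity.

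Harms are dealt with elsewhere, as matters of participant protection. Under Potential Risks, "In the case of acute soreness, the current training session will be ended", with conditions on resuming, and a list of symptoms stops participation during assessments and training. The same section gives a definition, "Here, serious adverse events are defined as any untoward medical occurrence that results in death, is life threatening", attached to a sentence about the laboratory's earlier work with more than 250 people. Section 2.b (Protection Against Risks) has the study Physical Therapist evaluate a participant who needs immediate treatment.

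Section 4 hopes to improve reactive postural control, "increase balance self-efficacy, and enable walking activity in those with chronic stroke and low falls self-efficacy". Of the step monitor, section 1.b item 10 says "Participants will wear the monitor for seven days"; this is repeated after the final assessment.

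**The concern.** The study recruits people with low balance confidence and hopes that they will become more confident and walk more. More walking away from the harness is also more exposure to falling. Whether falls rise, drop or stay the same is therefore a natural companion to the step count, and the plan has no stated means of finding out.

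A study run exactly as written could report good adherence and a favourable effect size for activity while falls at home and injuries that appear later were never asked about. Those events would be unknown, but a reader of the report could take silence for zero. The plan says the results may inform a later grant application, so the next study could inherit a harm profile that nobody measured.

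**Working it through.** **1. The plan's own counts.** Section 1.a: "A total of five participants with chronic stroke (i.e. 6 or more months after stroke) are expected to qualify for this study". Statistical Design and Power: "Of these participants, we estimate that two will not pass initial screening from the physical therapist or DXA scan". So 5 + 2 = 7 enrolled, as stated. Three assessments plus six training sessions give 3 + 6 = 9 laboratory visits, as stated in section 1.b item 1. Visits after baseline: 9 − 1 = 8. The plan disclaims inferential statistics, so there is no power figure to reproduce.

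**2. Where a harm could be recorded.**

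| Place in the plan | What it collects or does | Harm recorded as an outcome? |
|---|---|---|
| Adaptation | Protocol changes, perturbation number and size, adherence | No; accommodations only |
| Implementation | Factors in completion, perceived challenge and benefit | No; a harm may surface by chance |
| Limited Efficacy | Cohen's d, self-efficacy and activity | No |
| Assessment visits (1.b items 7–11, 13) | Surveys, clinical tests, stepping thresholds, step monitor | No stated question |
| Training sessions (1.b item 12g) | ABC and FES-I, which the plan uses as self-efficacy measures | No; neither is used as a count of falls |
| Final interview (1.b item 13) | Benefit, challenge, suggested changes | No stated question |
| Materials | List of data sources | No falls or adverse-event record named |
| Potential Risks | Stopping conditions, soreness rule | Management only |
| Protection Against Risks | Evaluation when immediate treatment is needed | Management only |

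Harms are thus in 0 of 3 domains, and a stated question on events since the last visit is in 0 of 8 post-baseline visits. After the last laboratory visit there are seven days of monitor wear with no stated safety question.

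**3. What a count could show.** With no events among n participants, the exact one-sided 95% upper limit for the true risk is 1 − 0.05^(1/n), and the two-sided limit is 1 − 0.025^(1/n).

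- n = 5: 1 − 0.05^(1/5) = 45.1%; two-sided 52.2%.
- n = 7, if all enrolled were trained: 34.8%; two-sided 41.0%.
- One affected participant of five: two-sided 95% interval 0.5% to 71.6%.

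The chance of seeing at least one affected participant among five is 1 − (1 − p)^5. The documents give no risk, so p is assumed over a range:

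| Assumed true risk p | Chance of at least one in five |
|---|---|
| 10% | 41% |
| 20% | 67% |
| 30% | 83% |
| 50% | 97% |

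A common harm would probably be seen if it were asked about. The absence of events would establish very little.

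**The case against.** The case on the other side has real force, and it limits what can be claimed. A reader might draw several stronger conclusions that the documents do not support.

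- *That someone who falls at home would count as a success on every domain.* The plan sets no success criterion. It is only that no domain is designed to register the event.
- *That soreness is wholly unseen.* The rule that sessions wait until soreness has gone, and that perturbations do not return to the level that caused it, requires staff to learn about soreness and remember the level. What is missing is a stated question and a reported record.
- *That accommodations go undocumented.* Adaptation already covers most of them, including perturbation size, breaks and hand support.
- *That the training raises falls.* Section 4 also hopes for better reactive control, which would be expected to reduce them. The documents give no fall rate, so the direction is open; that is a reason to count.
- *That the four failed responses in threshold testing are falls.* Participants are told not to step, so a failure is a step, taken in a harness.
- *That return of the last monitor is an existing contact.* The plan says only that participants are told how to return it.
- *That the control period offers an informative comparison of falls.* Control lasts about three weeks, the training period has no stated length, and five people are expected. Only description is possible.
- *That there is no adverse-event reporting at all.* Consent pages are not in the text, and institutional procedures may exist outside it.

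The central point survives all of these. Neither the domains, the visit procedures nor the data sources include a harm count, and incidental capture through an interview or a withdrawal does not reach a home fall in someone who completes training.

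**Conclusion.** The point holds as a gap in outcome definition and data collection. Run as written, the study could describe feasibility and changes in activity with falls and injuries outside the laboratory uncollected. It should be corrected, but it does not undermine the three domains for what they do measure.

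The conclusion rests on two assumptions: that the procedures and data sources listed are complete, and that any institutional reporting of adverse events does not feed the feasibility results. Nothing here suggests that the training is unsafe, and a full count in five participants could not show that it is safe.

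**What to change.** Add a fourth, descriptive domain, Safety and Tolerability.

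- At each of the eight post-baseline visits, ask one fixed set of questions about the time since the last visit: falls, injuries, soreness and medical contacts.
- Ask the same questions once when the final monitor is returned, by short form or call if the return is not in person.
- Record harness arrests and session stops, cross-referring to the accommodations already documented under Adaptation.
- Apply the serious adverse event definition under Potential Risks to this study.
- List events by participant, with counts and days at risk for the control and training periods. Take the days from actual visit dates, and state beforehand to which period the days between the second assessment and the first training session belong.
- Place these results beside any feasibility statement, as description only, with no comparison of periods by test and no conclusion of safety.

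This changes no training procedure, schedule or stopping rule. The cost is a few minutes per visit, one table, possibly one extra brief contact, and a less favourable report if events occur.
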